6.3 Chemotherapy Dose Modification

Dose modifications for carboplatin and etoposide are permitted for toxicity according to the prescribing information and local standard-of-care. Dose modification guidelines are provided below. Once reduced, the dose cannot be increased back to 100%.

Treatment with carboplatin or etoposide should be discontinued if a patient experiences any hematologic or non-hematologic Grade 3 or Grade 4 toxicity after two dose reductions or treatment is delayed for more than 63 days due to toxicities.

6.3.1 Criteria for start of Cycle

Prior to the start of each Cycle the following is required:

- ANC \geq 1500/uL
- Platelet count \geq 100,000/uL

6.3.2 Hematologic Toxicity

Treatment may be delayed for up to 63 days to allow sufficient time for recovery. Growth factors may be used in accordance with American Society of Clinical Oncology (ASCO) and NCCN guidelines (Smith et al. 2006; NCCN 2015). Upon recovery, dose adjustments at the start of a subsequent cycle will be made on the basis of the lowest platelet and neutrophil values from the previous cycle. See the Table below.

In the event that dose adjustments are needed for both ANC and platelets, patients are to receive the lower dose.

Toxicity ^a	Dose
ANC $<$ 500/ μ L and platelets \geq 50,000/ μ L	75% of previous dose
Platelets $<$ 25,000/ μ L, regardless of ANC	75% of previous dose
Platelets $<$ 50,000/ μ L with Grade \geq 2 bleeding, regardless of ANC	50% of previous dose
ANC $<$ 1000/ μ L plus fever of \geq 38.5°C	75% of previous dose

^a Nadir of prior cycle.

Investigators should be vigilant and alert to early and overt signs of myelosuppression, infection, or febrile neutropenia so that these complications can be promptly and appropriately managed. Patients should be made aware of these signs and encouraged to seek medical attention at the earliest opportunity.

If chemotherapy is withheld because of hematologic toxicity, full blood counts (including differential WBC) should be obtained weekly until the counts reach the lower limits for treatment as outlined. The treatment can then be resumed.

No dose reductions are recommended for anemia. Patients should be supported per the investigator's institution's guidelines.

6.3.3 Non-Hematologic Toxicity

For a non-hematologic toxicity, treatment may be delayed for up to 63 days until resolution to less than or equal to the patient's baseline value (or Grade ≤ 1 if the patient did not have that toxicity at baseline). Dose reductions at the start of the subsequent cycle should be made on the basis of non-hematologic toxicities from the dose administered in the preceding cycle. Recommended dose modifications for non-hematologic toxicities are in Table below.

Toxicity	Adjusted Dose as % of Previous Dose ^a	
Diarrhea	Grade 3 or 4 ^b	75%
Nausea/vomiting	Grade 3 or 4 ^c	75%
Neurotoxicity	Grade 2	75%
	Grade 3 or 4	50% or permanent discontinuation
Transaminase elevation	Grade 3	75%
	Grade 4	Discontinue
Other	Grade 3 or 4	75%

AUC = area under the concentration-time curve.

^a If deemed appropriate by the investigator, adjust carboplatin dose to the specified percentage of the previous AUC.

^b Grade 3 or 4 diarrhea that occurs on adequate anti-diarrhea medication or any grade of diarrhea requiring hospitalization.

^c Despite the use of anti-emetics.

Diarrhea should be controlled with adequate anti-diarrhea medication. Nausea and/or vomiting may be controlled with adequate anti-emetics. For Grade 3 or 4 neurotoxicity chemotherapy should be resumed at 50% of the previous dose upon improvement or discontinued immediately (based on investigator's clinical judgment).

Suggested recommendations for dose modification of etoposide for renal impairment are provided below.

Creatinine clearance (mL/min)	Etoposide Dose
>50	100%
15–50	75% of dose

6.4 Protocol Therapy Discontinuation

In addition to discontinuation from therapy related to toxicities as outlined above, a subject will also be discontinued from protocol therapy and followed per protocol under the following circumstances outlined below. The reason for discontinuation of protocol therapy will be documented on the electronic case report form (eCRF)

- Documented disease progression based on RECIST 1.1
- Site investigator determines a change of therapy would be in the best interest of the subject
- Subject requests to discontinue protocol therapy, whether due to unacceptable toxicity or for other reasons
 - In a subject decides to prematurely discontinue protocol therapy (“refuses treatment”), the subject should be asked if he or she may still be contacted for further scheduled study assessments. The outcome of that discussion should be documented in both the medical records and in the eCRF.
- Female subject becomes pregnant
- Protocol therapy is interrupted for ≥ 63 days.

6.5 Protocol Discontinuation

If a subject decides to discontinue from the protocol (and not just from protocol therapy) all efforts should be made to complete and report study assessments as thoroughly as possible. A complete final evaluation at the time of the subject's protocol withdrawal should be made with an explanation of why the subject is withdrawing from the protocol. If the reason for removal of a subject from the study is an adverse event, it will be recorded on the eCRF.

7. STUDY CALENDAR & EVALUATIONS

Study Evaluation Cycle = 21 days	Screening	On Treatment Cycles 1-4			Maintenance Cycles 5+	Safety follow up visit	Long-term Follow up
	-28 days	Day 1 ± 2 days	Day 2	Day 3	Day 1 ± 2 days	30 days post last dose + 7 days	Every 3 months (±14 days)
REQUIRED ASSESSMENTS							
Informed Consent	X						
Medical History	X						
Physical Exam	X	X			X	X	
Vital signs and ECOG Performance Status	X	X			X	X	
Quality of Life Questionnaires		x ³			x ³	x ³	
AEs & concomitant medications	X	X			X	X	
LABORATORY ASSESSMENTS							
Complete Blood Cell Count with diff (CBC)	X	x ⁹			X	X	
Comprehensive Metabolic Profile (CMP)	X	x ⁹			X	X	
PT/INR and aPTT	X						
Thyroid Function Testing	X	C3D1			x ⁴	X	
Hepatitis Testing	X						
Pregnancy test (serum or urine) (WOCBP)	X	x ⁴			x ⁴		
DISEASE ASSESSMENT							
CT of chest	x ⁵	C3D1			x ⁵		x ⁵
CT or MRI of abdomen and pelvis	x ⁵	C3D1			x ⁵		x ⁵
MRI Brain	x ⁵	C3D1			x ⁵		x ⁵
TREATMENT EXPOSURE							
Atezolizumab		D1			x ⁶		
Carboplatin		D1					
Etoposide		D1-D3					
SPECIMEN COLLECTION							
Archival Tumor Tissue	x ⁷						
Blood Samples		x ⁸				x ⁸	
FOLLOW-UP							
Survival Status, Subsequent Therapy							X

- 1: Medical History; other data to be obtained during this assessment includes a smoking history questionnaire and trial awareness question. In addition, prior anti-cancer treatment should be documented including medications (chemotherapy, checkpoint inhibitors, etc) radiation or surgery. In addition, diagnosis and staging to include pathology report and TNM staging documentation. Histological confirmation per VALG of Stage IV Stage Small Cell Lung Cancer (SCLC)- extensive stage. Prior genomic testing (ie NGS) and PD-L1 results are required if available.
- 2: Physical exam to include a complete neurological exam. Vital signs to include temperature, pulse, respirations, blood pressure weight, and height (screening only) and ECOG performance status.
- 3: Quality of life evaluations include FACT-Br, FACIT-Fatigue, and Godin Leisure-Time Exercise Questionnaire. Questionnaires to be completed Cycle 1 Day 1 then every other Cycle of treatment (6 weeks; \pm 1 week) and at the D30 Safety Visit.
- 4: CBC with platelet and differential (white blood cell count, absolute neutrophil count, hemoglobin and platelet count). Serum chemistries (creatinine, glucose, total bilirubin, aspartate transaminase [AST] and alanine transaminase [ALT] and calcium). Thyroid Function testing should be performed at screening then every 6 weeks (i.e. every other cycle). TSH will be obtained. T4 and T3 including free versus total testing is at the discretion of the site investigator. Hepatitis testing to be performed at screening if results as described in the inclusion criteria are not known. For women of childbearing potential (WOCBP): urine or serum β hCG if clinically appropriate. If a urine test is done and it is positive or cannot be confirmed as negative, a serum pregnancy test will be required. Testing is required within 24 hours prior to initiation of study treatment. During treatment, testing should be performed every 3 weeks (on Day 1 of each cycle prior to administering treatment).
- 5: Tumor response assessment will consist of evaluation by MRI scan of the brain and CT scans of chest +/- abdomen and pelvis. If unable to perform MRI due to medical reasons, CT with contrast is acceptable. Brain MRI used to diagnose brain metastases allowed or a CT with contrast is acceptable. The abdomen/pelvis may be scanned at follow-up timepoints only if positive disease was detected at baseline. Radiology imaging to be performed at screening (within 6 weeks prior to C1D1), then every 6 weeks (prior to Cycle 3 Day 1 and Cycle 6 Day 1) then every 9 weeks (prior to Cycle 9 and so on). Imaging needs to occur every time point regardless of any delay in treatment. Tumor imaging to be done in the follow up period is at discretion of site investigator. If tumor assessments are available for subjects who have not yet experienced progressive disease (PD) at the time treatment is discontinued, the follow-up tumor evaluations will be documented in the eCRF until PD or death is confirmed, or until another treatment is initiated.
- 6: Induction treatment will consist of 4 cycles of Atezolizumab (1200 mg on Day 1) combined with carboplatin (5-6 AUC on Day 1) and etoposide (80-100 mg/m² on Days 1-3). After 4 cycles of induction treatment, subjects will receive atezolizumab maintenance 1200 mg on Day 1 of each 3-week cycle. Subjects will receive treatment until disease progression, unacceptable drug-related toxicity, or withdrawal from study for any reason.
- 7: Archival tissue is required if available. Archival tissue should be identified and requested at screening and shipped by Cycle 2 Day 1, if available. If archival tissue is not available, the subject may still be eligible for the trial. See CLM for collection, labeling, and shipping instructions. Subjects will also be consented for optional storage of any remaining tissue samples after protocol-specified studies are complete. These samples will be stored for future unspecified cancer-related research and are considered “banking samples”.

8: Blood (whole blood for PBMCs, plasma and buffy coat for germline DNA) for correlative analysis will be drawn prior to treatment on Cycle 1 Day1, Cycle 3 Day 1 and at the D30 safety visit/progression. Additional details regarding correlatives can be found in Section 8 and the CLM.

9: If screening (baseline) CBC and Chemistry (CMP) were performed within 7 days of Day 1 of treatment, these do not need to be repeated. All laboratory assessments should be done prior to treatment.

10: Safety Follow Up: The safety follow-up visit should only occur when subjects permanently stop study treatment for whatever reasons (toxicity, progression, or other reason) and should be performed 30 days (+ 7 days) after the last dose of treatment. Subjects who have an ongoing Grade ≥ 2 or serious AE (SAE) at this visit will continue to be monitored by a member of the study team until the event is resolved, stabilized, determined to be irreversible by the site investigator or a new anti-cancer treatment starts, whichever occurs earlier.

11: Long Term Follow Up: For subjects who discontinue for reasons other than progressive disease, radiographic disease assessment should be performed every 9 weeks until progression, initiating a new cancer treatment, withdrawing consent or becoming lost to follow-up. The scan interval may be reset if scans were done sooner for clinical reasons and the type of scan may be left to discretion of the site investigator. This imaging may be done locally. Once disease progression is documented, subjects will be followed for survival every 3 months for 1 year from documented progression. Follow up may be accomplished via clinic visit, phone call, or other avenues as appropriate. A window of ± 14 days will be applied to follow up.

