Platinum and etoposide typically results in a very high initial response rate (~60-80%) and modest progression free survival (~4-6 months), with median overall survival of less than twelve months in the majority of patients [5-7]. Despite initial chemosensitivity, a hallmark of SCLC is the development recalcitrant behavior to subsequent lines of chemotherapy resulting in dismal outcomes in the refractory setting. Prophylactic cranial irradiation (PCI) has been studied and utilized extensively over the past several decades to improve outcomes by treating occult micrometastatic disease and reducing the incidence of brain metastases. A meta analysis of PCI in the limited stage setting, in SCLC demonstrated a marked reduction in brain metastases from 59% to 33% and improved 3 year survival from 15.3 to 20.7 months [8]. However, in ES SCLC, data regarding the role of PCI has been conflicting. The initial phase III EORTC study of 286 patients randomized PCI or observation following initial 4-6 cycles of chemotherapy [9]. While the incidence of symptomatic brain metastases and survival improved in the PCI arm, the results were criticized as MRI was not routinely performed prior to PCI and therefore likely included a portion of patients with brain metastases. In a separate study from Japan, 224 patients with response to chemotherapy were randomized to receive either PCI or observation [10]. All patients had a baseline MRI prior to enrollment and every 3 months during follow up. The study was stopped early due to futility and a trend was noted with worse survival in patient receiving PCI compared with observation.

In March 2019, the anti-PD-L1 antibody atezolizumab combined with carboplatin and etoposide, a topoisomerase II inhibitor, was FDA-approved for first-line treatment of ES SCLC [11]. This priority approval was based on the results of the IMpower133 study (NCT02763579), a trial which allowed but was not specifically designed for patients with brain metastases. As a result, of the 403 patients, only 35 (9%) had brain metastases. Additionally, recent results from the CASPIAN study of chemotherapy with or without durvalumab included approximately 10% of patients with brain metastases [12]. Thus, limited data exists currently regarding clinical outcomes of patients with SCLC and brain metastases at time of diagnosis.

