9.2 Definitions for Response Evaluation – RANO -BM

MRI scan of head at screening and every other treatment cycle (i.e. 6 weeks) through week 48, then every 9 weeks (i.e. every 3 cycles) until documented disease progression starting after treatment initiation with Cycle 1. Given that imaging following immunotherapy differs greatly from what is typically seen following chemoradiation treatment or treatment with anti-angiogenic compounds, evaluation of response using Macdonald criteria or Response Assessment in Neuro-Oncology (RANO) criteria is not appropriate in this trial. Due to differences in the nature of primary brain tumors and brain metastases, a modified version of RANO called RANO-BM will be used.

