9.2.4 Evaluation of non-target lesions

Complete Response (CR)	Requires all of the following: disappearance of all enhancing CNS non-target lesions, no new CNS lesions.
Non-CR/ Non-PD	Persistence of one or more non-target CNS lesion or lesions.
Progressive Disease (PD)	Any of the following: unequivocal progression of existing enhancing non-target CNS lesions, new lesion(s) (except while on immunotherapy-based treatment), or unequivocal progression of existing tumor-related non-enhancing (T2/FLAIR) CNS lesions. In the case of immunotherapy-based treatment, new lesions alone may not constitute progressive disease.

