9.2.5 Evaluation of best overall CNS response

Target Lesions	Non-Target Lesions	New Lesions**	Corticosteroids	Clinical status	Overall Response
None	None	None	None	Stable or improved	CR
≥30% decrease in sum longest distance relative to baseline	Stable or improved	None	Stable or decreased	Stable or improved	PR
<30% decrease relative to baseline but <20% increase in sum longest distance relative to nadir	Stable or improved	None	Stable or decreased	Stable or improved	SD

$\geq 20\%$ increase in sum longest distance relative to nadir*	Uequivocal progressive disease*	Present*	N/A	Worse*	PD

*Progression occurs when any of these criteria are met. If ≤ 6 months from initiation of immunotherapy, radiographic progression (including new lesions) with no new or significantly worsened neurologic deficits not due to co-morbid event or concurrent medication should be confirmed on follow-up imaging 3 months after initial radiographic progression (if progression confirmed, the date of actual progression should be back-dated to the date of initial radiographic progression). **A new lesion is one that is not present on prior scans and is visible in minimum two projections. If a new lesion is equivocal, for example because of its small size, continued therapy can be considered, and follow-up assessment will clarify if the new lesion is new disease. If repeat scans confirm there is definitely a new lesion, progression should be declared using the date of the initial scan showing the new lesion.
					

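### A contrast CT can serve as the baseline brain scan while follow-up is by MRI, with no same-modality rule, so a lesion CT missed can count as intracranial progression at about week 6

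*Combined protocol and SAP*

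**What the plan says.** The protocol addresses the brain scan in several places.

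- **Section 7, footnote 5, default:** "Tumor response assessment will consist of evaluation by MRI scan of the brain". The calendar row is likewise labelled as brain MRI.
- **Footnote 5, exception:** "If unable to perform MRI due to medical reasons, CT with contrast is acceptable".
- **Footnote 5, next sentence:** "Brain MRI used to diagnose brain metastases allowed or a CT with contrast is acceptable". No medical reason is attached here.
- **Footnote 5, timing:** after screening, "then every 6 weeks (prior to Cycle 3 Day 1 and Cycle 6 Day 1", so the first on-treatment brain scan falls at about week 6.
- **Section 9.2:** "MRI scan of head at screening and every other treatment cycle". No CT alternative is named.
- **Section 9.2.4:** "In the case of immunotherapy-based treatment, new lesions alone may not constitute progressive disease".
- **Section 9.2.5, definition:** "A new lesion is one that is not present on prior scans and is visible in minimum two projections". Its table lists a new lesion among the criteria any one of which is progression.
- **Section 9.2.5, confirmation:** within 6 months of starting immunotherapy, radiographic progression without new or significantly worsened neurologic deficit is to be confirmed 3 months later. If confirmed, it is back-dated to the first scan that showed it.

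The primary endpoint, iPFS, is intracranial progression by RANO-BM or death (Sections 2.2.1 and 12.2.1).

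**The concern.** If the baseline is a CT and the first follow-up is an MRI, the two scans differ in more than time. A lesion that was there on Day 1 but not visible on CT will be absent from the prior scans and present on the first MRI. Under the 9.2.5 definition it is new, although nothing has grown.

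Such events would cluster at the first assessment and would all shorten iPFS. The trial aims to separate a median of 5.2 from 4.0 months with 60 patients (Section 12.3) and has a futility look at about 29 events (Section 12.7), so a few early false events could matter. The analysis plan for iPFS (Section 12.6.1) contains no sensitivity analysis by imaging modality.

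**Working it through.** **Step 1. Does the text allow a CT baseline followed by MRI?** The first CT sentence in footnote 5 is conditional on a medical reason; the second is not. If the second only repeated the first it would be redundant, so a site can fairly read it as a separate route. Section 9.2 and the calendar row point to MRI at screening, so the passages disagree. No section requires the same modality across scans, and footnote 11 leaves the type of scan in long-term follow-up to the site investigator.

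**Step 2. Can this become an iPFS event?** The 9.2.5 definition of a new lesion has no same-modality condition. Section 9.2.4 makes an exception for new lesions during immunotherapy, and every patient receives atezolizumab from Day 1. Section 9.2.5 nevertheless counts new lesions as progression and, if repeat scans confirm one, dates progression to the first scan. A pre-existing lesion that is still visible 3 months later can be confirmed in this way. So the path is open, but conditional on persistence and on which of the two sections is followed.

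**Step 3. Reproduce the plan's power.** Inputs from Section 12.3: n = 60, medians 4.0 and 5.2 months, exponential survival, 22 months' accrual, 12 months' follow-up, one-sided alpha 0.15. The one-sample log-rank statistic is Z = (O − E)/√E, where E = Σ λ0·Xi, λ0 = ln 2/4.0 and Xi is time on study.

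- Analytic power: 80.2% with variance E; 81.7% with variance (O + E)/2.
- Simulation (40,000 trials): 81.4% and 82.2%.
- Stated: approximately 81%. It reproduces.

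(A separate matter: the stated event probability of 0.9707 corresponds to 18 months' follow-up; 12 months gives 0.9348. Analytic power with variance E changes only from 80.2% to 80.7%.)

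**Step 4. Add false week-6 progressions.** Let g be the share of patients assigned a false progression at 6 weeks (1.38 months) unless a true event came first. At a true median of 5.2 months, exp(−ln 2 × 1.38/5.2) = 0.832 are still event-free then, so 3 patients assigned means about 2.5 events actually moved. Beyond 1.38 months the apparent curve is (1 − g)·exp(−λ1·t) with λ1 = ln 2/5.2, so

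apparent median = 5.2 × [1 + log2(1 − g)].

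For g = 0.05: log2(0.95) = −0.074, and 5.2 × 0.926 = 4.82 months.

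| Patients assigned, of 60 | g | Apparent median (months) | Power (simulated, variance E) |
|---|---|---|---|
| 0 | 0% | 5.2 | 81.4% |
| 1 | 1.7% | 5.08 | 78.0% |
| 2 | 3.3% | 4.95 | 74.3% |
| 3 | 5% | 4.82 | 70.4% |
| 6 | 10% | 4.41 | 57.5% |

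Each of the first three patients costs about 0.13 months and 3 to 4 points of power. With a true median of 4.0 months, the rejection rate falls from 14.1% to 8.4% at g = 5%. The effect on the futility look was not calculated.

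**Step 5. What would g be?** g = (share with CT baseline) × (share of those with a missed lesion called new) × (share confirmed). None of the three is in the documents. Assumed values for the first two of 10% × 25%, 10% × 50%, 20% × 50% and 30% × 50%, all confirmed, give g = 2.5%, 5%, 10% and 15%, and medians of 5.0, 4.8, 4.4 and 4.0 months. If only half are confirmed (also assumed), the first and last become g = 1.25% and 7.5%, with medians of about 5.1 and 4.6 months.

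**The case against.** The strongest case on the other side has five parts.

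- **The safeguards.** A new lesion at week 6 is not scored as progression at once. The 9.2.4 exception covers every patient in this trial, and 9.2.5 asks for confirmation. Section 1.2 says chemotherapy can produce intracranial response in the majority of patients, although one 24-patient series showed 27%. Some missed lesions will therefore be gone by the confirmatory scan. This stands: the false event is possible, not automatic. It does not close the gap, because a persisting lesion can be confirmed and back-dated, and 9.2.4 and 9.2.5 disagree on whether new lesions alone count.
- **A narrower reading of footnote 5.** The disputed sentence follows the medical-reason exception and may only mean that the diagnostic scan can serve as baseline, with the same CT fallback. That is a fair reading, but the sentence does not say so. How often sites would use the wider one is unknown. Patients followed by CT throughout have no change of modality.
- **The evidence on CT.** Section 1.1 reports that an earlier PCI trial was criticised because "MRI was not routinely performed prior to PCI and therefore likely included a portion of patients with brain metastases". That concerns scans not routinely done. It does not compare contrast CT with MRI and supports no particular miss rate.
- **Direction.** The bias works against the regimen and cannot produce a false claim of efficacy. This stands.
- **Leptomeningeal disease.** A reader might also infer that a CT baseline weakens this exclusion. Exclusion 2 names no modality, so the documents do not settle that.

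**Conclusion.** The defect is real: footnote 5 and Section 9.2 differ on the screening modality, no same-modality rule exists, and a lesion unseen on a baseline CT can end as an intracranial progression dated to about week 6. The consequence is a downward bias in iPFS and a loss of power.

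The size cannot be stated from the documents. Three patients of 60 would take the median from 5.2 to about 4.8 months, roughly a third of the 1.2-month difference the trial is designed to detect, and power to about 70%. This rests on exponential iPFS, a true median of 5.2 months and an assumed share of false week-6 progressions.

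A reader might infer that the apparent median could fall to 4.0 months, the null value. That requires the top of both assumed ranges (30% CT baselines, 50% with a missed lesion) and complete failure of both safeguards. It is an upper bound, not a forecast. Should-fix, moderate confidence.

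**What to change.** 1. In footnote 5, delete the CT alternative from the baseline sentence so that it agrees with Section 9.2. Keep the existing exception for patients who cannot have MRI for medical reasons, and use CT at every time point for them.
2. In Section 9.2.5, state that a lesion first seen after a change of modality is not new until it is compared with an earlier scan of the same modality.
3. Reconcile 9.2.4 with 9.2.5 on whether new lesions alone constitute progression during immunotherapy.
4. For patients already enrolled with a CT baseline and MRI follow-up, add an iPFS sensitivity analysis that excludes them. Define the group at baseline (CT baseline with no medical bar to MRI), so that exclusion does not depend on reaching the first MRI.

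**Cost.** Items 1 to 3 are wording, and the screening MRI is already required by Section 9.2. Patients who had only a CT may face some screening delay. Inclusion criterion 6 allows one chemotherapy cycle within 30 days before enrolment, so for some of them the baseline MRI may follow that cycle, which affects later comparisons with baseline. Under item 2, a lesion that truly arose between a CT baseline and the first MRI would not count as new at that scan; item 4 shows how much those patients matter.
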